## 6.1 ADMINISTRATIVE PROCEDURES

Data of therapy will be entered into a case report form (CRF).

## 6.2 GENERAL INFORMED CONSENT

This study is non-interventional, and no additional procedures will be performed on the patient in addition to the normal real-world clinical practice of the treating physician. Informed consent will be obtained from all patients for their clinical data to be recorded pseudonymously and to collect PRO measures. Patients will also be informed of their right to withdraw their consent at any time during the study. The physician or a qualified person designated by the physician, should fully inform the patient of all pertinent aspects of the study. The written informed consent document must be prepared and provided in the language(s) of the potential patient population. Patients must understand that it is their own free will to participate and that they can withdraw consent at any time without giving reasons and without penalty or loss of benefits to which the subject is entitled. The patient will be given ample time and opportunity to obtain answers to any open questions. All questions relating should be answered to the satisfaction of the patient. The written consent form will be personally dated and signed by the patient and the by investigator conducting the informed consent discussion. The informed consent forms will be filed in the patient's record. A copy of the signed and dated

Product: Vertigoheel Observational Plan Version: 1 – 27MAY2021

informed consent form will be given to the patient.

## 6.3 MEDICAL HISTORY

#### **Medical History/Demographics**

A medical history will be obtained by the investigator or qualified designee. Alcohol, drug, and any substance abuse history will also be documented. Demographic data will be collected.

#### 6.4 PRIOR AND CONCOMITANT MEDICATIONS REVIEW

#### **Concomitant Medications**

All medication taken by the patient within two weeks prior to the start of treatment with Vertigoheel® and all concomitant medications taken by the patient during this study must be recorded in the source documents and in the eCRF.

#### Medication

Treatment with Vertigoheel® will be documented in detail (dosing, dose adjustments, and dates of administration).

#### Termination of Vertigoheel® treatment

When a patient discontinues/withdraws prior to the study completion, all applicable activities scheduled for the final study visit should be performed at the time of discontinuation.

#### 6.5 CLINICAL PROCEDURES/ ASSESSMENT

A complete physical examination performed by the principal investigator includes the following assessments: general appearance, head, eyes, ears/nose/throat, head/neck/thyroid gland, lymph nodes, skin, lungs, heart, abdomen, musculoskeletal, and neurologic evaluations. Breast, rectal, and genitourinary/pelvic exams should be performed when clinically indicated. The patient's weight and vital signs should be included in the assessment.

#### 6.6 OTHER PROCEDURES

#### **Patient Number**

All consented patients will be given a unique depersonalized identification number. The patient number identifies the patient for all procedures occurring during observation. Data protection and other applicable regulatory requirements will be fulfilled.

#### **Patient Reported Outcome**

DHI, PHQ-9, GAD-7 and QoL questionnaire EQ-5D-5L will be collected.

#### **Eligibility Criteria Review**

The eligibility criteria must be reviewed by the investigator to ensure that the patient qualifies for the study.

#### **Adverse Events**

The investigator must document all AE/SAE. He/she must also determine the severity and relationship to study medication of all AE/SAEs. For further instructions please refer to Chapter 9, Assessment and Reporting of Adverse Events.

#### **Unscheduled Visits**

Unscheduled visits may be performed at any time at the discretion of the investigator to ensure patient safety.

#### End of follow-up

Patients will be followed until:

- End of month  $2 \pm 1$  observational period for the patient.
- Death.
- Withdrawal of consent.

## 7 SAFETY REPORTING AND RELATED PROCEDURES

#### Introduction

This is a primary data collection non-interventional study being conducted within routine medical practice. All direction for medication usage is at the discretion of a physician in accordance with usual medical practice. No administration of any therapeutic or prophylactic agent is required in this protocol, and there are no procedures required as part of this protocol.

### 7.1 ADVERSE EVENT DEFINITIONS AND REPORTING

### Definitions

#### Adverse Event

An Adverse Event/Experience (AE) is any untoward medical occurrence in a patient or in a clinical investigation subject administered a pharmaceutical product and which does not necessarily have a causal relationship with this treatment. An AE can therefore be any unfavorable and unintended sign (including an abnormal laboratory finding), symptom or disease temporally associated with the use of a medicinal product, whether related to the treatment.

In the pre-approval clinical experience with a new medicinal product or its new usages, particularly as the therapeutic dose(s) may not be established: all noxious and unintended responses to a medicinal product related to any dose should be considered adverse drug reactions.

### **Serious Adverse Event**

Any untoward medical occurrence:

• results in death

- is life-threatening
- requires unscheduled inpatient hospitalization or prolongs an existing hospitalization
- results in persistent or significant disability/incapacity or
- is a congenital anomaly/birth defect
- is qualified as another medically significant event or condition

### **Recording Adverse Events**

For adverse event recording, the study period is defined for each patient as the time from signing of the informed consent form through the end of the observation period (including the follow-up period). All adverse events, that occur during the defined study period must be recorded in the eCRF on the respective Adverse Event Report Form, regardless of the severity of the event or the relationship to Vertigoheel®. The AEs related to Vertigoheel® should be reported to Heel monthly.

For serious adverse events, related non-serious adverse events, the Adverse Event Form must also be completed, and the adverse event must be recorded and reported within 24 hours of becoming aware to Heel Drug Safety Management (FON [name] or [contact]). The investigator should evaluate all adverse events according to the criteria and steps mentioned below.

### Assessment of Intensity

Any adverse event must be graded regarding its intensity as follows:

MILD	Does not interfere with subject's usual function, easily tolerated.
MODERATE	Interferes to some extent with subject's usual function.
SEVERE	Interferes significantly with subject's usual function, incapacitating with inability to work or carry out usual activity.

#### Assessment of Seriousness

Determination of the seriousness of the adverse event according to the definitions for a serious adverse event (SAE).

### Assessment of Causality

Determination of the relationship of the adverse events to the medicinal product(s) being studied after having evaluated all accessible data according to the following classification:

NOT	Adverse events for which a reasonable explanation for an alternative cause is
RELATED	considered plausible, e.g. no study drug taken, plausible clinical alternative like accidental injury, pharmacologically incompatible temporal relationship or intercurrent illness.
RELATED	Adverse event for which a reasonably possible clinical and/or pharmacological relationship to study drug cannot be excluded, e.g. lacking plausible alternatives.

When the final causality assessment is unknown and it is uncertain whether the investigational

product caused the event, then the event should be handled as related to the investigational product for reporting purposes.

*Collection of Product Name and Batch Number of Medicinal Product* At each visit, the brand name and the batch number of the used medicinal product should be collected and documented in the eCRF.

## Pregnancy

All pregnancies of women participating in the study that occur during the study or within 6 months of the last dose of Vertigoheel® are to be reported to Heel by the physician within 24 hours of awareness. This also includes pregnancies without an adverse event. The pregnancy should be followed up to determine the outcome including spontaneous or voluntary termination, details of birth, and the presence or absence of any birth defect, congenital abnormalities or maternal, and newborn complications.

Pregnancies in partners of male patients will be recorded and monitored. The pregnant partner will be asked to sign an informed consent form, and the pregnancy will be followed as any other pregnancy would be.

## **PRODUCT COMPLAINTS**

A product complaint is defined as any report indicating a possible deviation from the product specification. These reports may concern packaging, labeling, medical devices, or drug products. Product complaints may include, but are not limited to, the following:

A product complaint is defined as any report indicating a possible deviation from the product specification. These reports may concern packaging, labeling, medical devices, or drug products. Product complaints may include, but are not limited to, the following:

- missing or extra units (e.g., primary container is received with more or less than the designated number of units inside)
- incorrect packaging, or incorrect or missing labeling/label
- unexpected or unanticipated taste, odor, or both
- suspicion of falsified medicines

If a product complaint is identified for a Vertigoheel® during the study, the investigator should contact Biologische Heilmittel GmbH (FON [name] or [contact]) within 48 hours of becoming aware of the issue.

## 8 STATISTICAL ANALYSIS PLAN

Due to the non-interventional design, this study is set-up for descriptive purposes, no a priori hypothesis will be tested, and no comparisons will be made with other products or treatments. Data will be analyzed by a contract CRO.

This is a non-interventional study. It is planned that 20 patients with BVP and 40 patients with FD (larger than in BVP due to inhomogeneity of the disease) participate in the observational period for

2-months treatment  $\pm 1$  month. Due to small number of patients enrolled, no interim analysis is planned.

### Sample Size Calculation

Sample size calculations have been performed for confidence intervals for different paired means. When the sample size is 20, a two-sided 95% CI for the difference between paired means will extend 0.351 from the observed difference in means. For a smaller CI a higher n is needed, i.e. n=25 (28 with 10% drop-out) distance from mean to limit 0.314, n=30 (33 with 10% drop-out) distance from mean to limit 0.265, n=40 (44) – 0.248.

- Significance level 0.05 (2-sided).
- 95% confidence intervals will be calculated to estimate treatment effects.
- Standard deviation of 0.8 for both indications.
- Lost to follow-up 10%.
- Power: 80%.

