Milestones	
 
under observation.
 
Unwilling or unable to comply with all the requirements of the study protocol.
 
Any relationship of dependence with the sponsor or with the investigator.
 
Sept 21 FPI, July 22 LPO, DBL Aug 22.
 

Statistical Methods	
 
Previous trial with Vertigoheel®
 
Weiser et al. (1998) The efficacy and safety evaluation of Vertigoheel® vs betahistine hydrochloride demonstrated a reduction of 2 score points of the mean intensity of vertigo attacks with a standard deviation of 0.8 score points and a non-inferiority limit of 20%. Power: 80%.
 
Current study
 
Significance level 0.05 (2-sided)
 
95% confidence intervals will be calculated to estimate treatment effects
 
Standard deviation of 0.8 for both indications
 
Lost to follow-up 10% (BVP) or 20% to 30% (FD) Power: 80%
 
(Please see 8.1)
 

Sample Size Calculations and Power Calculations	Sample size calculations have been performed for confidence intervals for different paired means. When the sample size is 20, a two-sided 95% CI for the difference between paired means will extend 0.351 from the observed difference in means. For a smaller CI a higher n is needed, i.e. $n=25$ (28 with 10% drop-out) distance from mean to limit 0.314, $n=30$ (33 with 10% drop-out) distance from mean to limit 0.265, n=40 (44) – 0.248.

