### **3.2 STUDY POPULATION**

Patients with BVP and FD will be recruited from the Department of Neurology in the German Center for Vertigo and Balance Disorders at the Hospital of the LMU, Munich.

As this is a prospective, non-interventional study, the study population will be composed of male and female patients, aged between 18 and 80 years old, diagnosed with BVP or FD. There are no specific patient withdrawal criteria for this non-interventional study except for the common ones such as loss of market authorization. A patient who is enrolled but does not complete the observational period may be replaced if study entry by end-April 2022.

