5.1 Sample Size Calculation

Sample size calculations were performed for confidence intervals for different paired means. When the sample size is 20, a two-sided 95% CI for the difference between paired means will extend 0.351 from the observed difference in means. For a smaller CI a higher n is needed, i.e. n=25 (28 with 10% drop-out) distance from mean to limit 0.314, n=30 (33 with 10% drop-out) distance from mean to limit 0.265, n=40 (44) – 0.248.

- Significance level 0.05 (2-sided)
- 95% confidence intervals will be calculated to estimate treatment effects
- Standard deviation of 0.8 for both indications
- Lost to follow-up 10%
- Power: 80%

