5.4 Data Analysis

SAS or R software, or an equivalent software package will be used for statistical analysis.

Descriptive statistics will be provided for all parameters. The statistics will be appropriate for the type of data:

- For continuous and count variables, statistics will include the number of observations, mean, standard deviation, median, minimum, maximum, and two-sided 95% confidence interval (CI).

- For categorical variables, the descriptive statistics will include the count and percent of observations in each category along with its Clopper-Pearson two-sided 95% CI. The denominator for the percentage calculation will be based on the number of patients in the analysis population.

This is a non-interventional, observational study, therefore only CI are calculated. All endpoints will be analyzed by the appropriate type of descriptive statistic(s) as described above.

All variables will be analyzed in an exploratory manner. No formal statistical hypothesis testing will be performed.

Missing values will not be imputed.

The following subgroups will be defined:

- Patients with FD
- Patients with BVP

It is planned to include 20 patients with BVP and 40 patients with FD.

No further subgroups will be defined.

Shift tables for physical examination, DHI, Posturography, and vHIT will display the number and percentage of patients per baseline value category vs. the worst value category post-baseline

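### With SD 0.8 the n=30 half-width is 0.286, not 0.265; the FD loss rates conflict, and expected precision for 20 BVP and 40 FD patients after losses is not given

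*Protocol*

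**What the plan says.** The same sample-size paragraph stands in the Protocol summary, in Protocol section 8 (Sample Size Calculation) and in SAP 5.1. It gives half-widths of the two-sided 95% CI for a paired mean difference, with an SD of 0.8 for both indications: 0.351 at n=20, 0.314 at n=25, and then "n=30 (33 with 10% drop-out) distance from mean to limit 0.265, n=40 (44) – 0.248". The 0.265 is identical in the summary ("33 with 10% drop-out) distance from mean to limit 0.265") and in the SAP ("n=30 (33 with 10% drop-out) distance from mean to limit 0.265").

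On loss to follow-up, the Statistical Methods row of the summary reads "Lost to follow-up 10% (BVP) or 20% to 30% (FD"). Protocol section 8 and SAP 5.1 give a single rate of 10% that does not distinguish the indications.

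On numbers, SAP 5.4 states: "It is planned to include 20 patients with BVP and 40 patients with FD". The same section states: "Missing values will not be imputed". Protocol 3.2 allows replacement: "A patient who is enrolled but does not complete the observational period may be replaced if study entry by end-April 2022". Protocol 6.4 asks that final-visit activities be done when a patient discontinues early.

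**The concern.** Half-widths at a fixed SD and confidence level must shrink in proportion to 1/√n. The n=30 value falls too far below the n=25 value and sits too close to the n=40 value to fit that pattern.

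The second problem is that a reader cannot tell whether the plan expects to lose 10% or up to 30% of the FD group, which makes up 40 of the 60 patients.

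The third is that the paragraph's own notation separates evaluable patients from the larger number to be enrolled: 25 (28), 30 (33), 40 (44). On that notation 0.248 belongs to 40 evaluable patients, which would need 44 enrolled, and the n=20 entry has no drop-out allowance at all. Yet 20 and 40 are the numbers to be included.

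Both documents rule out hypothesis testing and report only confidence intervals, so CI width is the whole basis for the sample size. The stake is whether that statement of precision is correct and usable.

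**Working it through.** **Inputs.** SD 0.8, two-sided 95% level, and stated half-widths at n=20, 25, 30 and 40 (Protocol section 8; same in the summary and SAP 5.1). Loss rates: 10% for BVP in all three places; for FD, 20% to 30% (summary) or 10% (section 8, SAP 5.1). Planned inclusion: 20 BVP and 40 FD. The stated power of 80% does not enter a CI half-width.

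**Step 1: reproduce the plan's figures.** Half-width = 1.96 × 0.8/√n.

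| n | Computed | Stated |
|---|---|---|
| 20 | 0.351 | 0.351 |
| 25 | 0.314 | 0.314 |
| 30 | 0.286 | 0.265 |
| 40 | 0.248 | 0.248 |

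Three of the four agree to three decimals, so the normal quantile is evidently what the authors used. The n=30 value does not agree: 0.286/0.265 = 1.08, so the true half-width is 8% wider than stated.

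**Step 2: look for another explanation.** Scaling from the plan's other entries, without using the SD, gives the same answer:
- 0.351 × √(20/30) = 0.287
- 0.314 × √(25/30) = 0.287
- 0.248 × √(40/30) = 0.286

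Other formulas at n=30 also fail to give 0.265: two-sided t, 0.299; one-sided normal, 0.240; one-sided t, 0.248; t with 80% assurance, 0.329. Using the inflated number 33 gives 0.273 (normal) or 0.284 (t). Solving for n gives (1.96 × 0.8/0.265)² = 35.0, so 0.265 is the n=35 value. The bracketed 33 equals 30 × 1.1, so the entry is meant for n=30 and the half-width is the wrong number.

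**Step 3: compare the loss rates.** BVP is 10% in all three places. FD is 20% to 30% in the summary and 10% in section 8 and SAP 5.1. The conflict therefore concerns FD only.

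**Step 4: precision after losses.** The ITT set (SAP 5.5) requires a dose and a measurement after baseline, and nothing is imputed. A patient lost before Visit 1 with no later measurement therefore contributes nothing to the change-from-baseline interval. If such patients are also not replaced:

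| Group | Included | Loss | Evaluable | Half-width | Listed value | Widening |
|---|---|---|---|---|---|---|
| BVP | 20 | 10% | 20 × 0.9 = 18 | 0.370 | 0.351 | √(20/18) = 1.054 |
| FD | 40 | 10% | 40 × 0.9 = 36 | 0.261 | 0.248 | √(40/36) = 1.054 |
| FD | 40 | 20% | 40 × 0.8 = 32 | 0.277 | 0.248 | √(40/32) = 1.118 |
| FD | 40 | 30% | 40 × 0.7 = 28 | 0.296 | 0.248 | √(40/28) = 1.195 |

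None of these four half-widths appears in the plan. The 28 in the text is the inflated enrolment for n=25, not an evaluable number.

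**The case against.** The first two parts are hard to dispute. The strongest case is against the third. Protocol section 8 and SAP section 5 describe 20 and 40 patients as taking part in the observation period, and non-completers may be replaced. Entry by end-April 2022 plus the maximum of three months reaches end-July 2022, the planned last visit, so the cut-off may be no more than the practical entry deadline. On that reading 20 and 40 are targets for observed patients, and 0.351 and 0.248 are the planned half-widths. Early stoppers may also be measured at discontinuation. This stands as a limit: the widened figures are conditional. It does not remove the gap, because replacement is optional, the sample-size text does not mention it, and the bracketed 44 shows that the authors themselves allowed for losses on top of 40.

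A second objection is that a t quantile would be more usual at these sizes. It would give 0.398 for BVP at n=18, and 0.271, 0.288 and 0.310 for FD at n=36, 32 and 28. That is true, and for BVP the move from normal to t (0.398/0.370, about 8%) is larger than the 5% from drop-out. The figures above keep the plan's own quantile so that they compare directly with its stated values.

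Third, 0.265 might come from a dropped n=35 row rather than a miscalculation. That is possible, but the n=30 figure is wrong either way.

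Finally, the SD of 0.8 comes from a vertigo-attack intensity score, while the primary endpoint is the DHI total on a 0 to 100 scale. This is correct, but it is a separate matter that the present correction does not settle.

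**Conclusion.** The concern holds and is minor. The n=30 half-width is wrong in all three places: 0.286 against 0.265 stated, 8% wider. The FD loss rate is contradictory: 20% to 30% against 10%. Both conclusions are firm.

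The precision expected from the planned inclusion is not stated. If lost patients are neither measured nor replaced, the half-width is 5% wider than listed for BVP and 5% to 20% wider for FD, depending on which loss rate applies. These figures rest on the plan's normal quantile and on 0.8 as the SD of the paired change. They do not show that this SD applies to the DHI total.

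The consequence is limited because nothing is tested, n=30 is not a chosen group size, and enrolment is unaffected.

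**What to change.** In the Protocol summary, Protocol section 8 and SAP 5.1:

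1. Change the n=30 half-width from 0.265 to 0.286. It is worth checking the original calculation output first; if an n=35 row was dropped, 0.265 can be restored beside n=35.
2. Reconcile the loss-to-follow-up rate for each indication and state the same rates in all three places.
3. Add one sentence giving the expected evaluable number and half-width for 20 BVP and 40 FD patients included, at the reconciled rates: BVP at 10%, 18 and 0.370; FD at 10%, 36 and 0.261; at 20%, 32 and 0.277; at 30%, 28 and 0.296. Say that the normal quantile is used and whether replacement is assumed.

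The cost is an edit to one paragraph in three places, plus the loss-rate line in the summary. Enrolment and procedures do not change. The only downside is that the stated precision becomes slightly less favourable.

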	sensation of vertigo and dizziness as change from baseline
	to month $2\pm 1$ assessed by the Dizziness Handicap
	Inventory (DHI; total).
Secondary Endpoints	• Effect of Vertigoheel ® on QoL as change from baseline to
	month $2\pm 1$ assessed by EQ-5D-5L.
	• Effect of Vertigoheel ® on total sway path as change from
	baseline to month $2\pm 1$ assessed by static posturography.
	• In FD effect of Vertigoheel ® on psychiatric symptoms as
	change from baseline to month $2\pm 1$ assessed by Patient
	Health Ouestionnaire Mood Scale (PHO-9) and
	Generalized Anxiety Disorder Screener (GAD-7)
	• In BVP effect of Vertigoheel ® on vestibular function as
	change from baseline to month 2+1 assessed by video
	head impulse test (vHIT) and/or caloric testing
	• Adverse events (AFs)
	
 
Other observations related to safety (physical examination)
 

	and vital signs)
Study Design	Non-interventional observational prospective monocentric
Study Design	study
Study Population	It is planned to include 20 patients with BVP and 40 patients
	with ED who are going to start Vertigoheel ® treatment
	according to clinical practice at the study conter
	The desision of treatment is up to the physician's discretion
	The decision of treatment is up to the physician's discretion
Inclusion / Evolusion	and is to be made independent of this study.
Criteria	Following documentation criteria should be fulfilled
Cintoina	• BVP (according to the diagnostic criteria of the Bárány
	Society) or FD (according to the diagnostic criteria of the
	Bárány Society).
	• Symptoms for > 3 months of moderate to severe intensity
	according to the DHI [0 (minimum score) -100 (maximum
	score)] of 30 to 90 points.
	• $\geq 18 - 80$ years of age.
	• Legally competent male or female outpatient.
	Signed informed consent.
	• Not pregnant (as proven by negative pregnancy test in
	case of woman of childbearing potential before first
	study drug administration) or breast-feeding.
	Patients with the following conditions are excluded from the
	documentation in this NIS
	• Ongoing (within the last two months) or recently started
	Vertigoheel ® treatment.
	• Debilitating acute or chronic illness (e.g. psychiatric
1	
	illnesses).

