### **3.4 INCLUSION CRITERIA**

Patients will be included in the study if they meet all the following criteria:

- Treatment with Vertigoheel® has been chosen by the physician independently of including the patient in this non-interventional study.
- BVP (according to the current diagnostic criteria of the Bárány Society, 2017) or FD (according to the diagnostic criteria of the Bárány Society, 2017)
- Symptoms for > 3 months of moderate to severe intensity according to the DHI [0 (minimum score) -100 (maximum score)] between 30 to 90 points.
- $\geq 18 80$  years of age.
- Legally competent male or female outpatient.
- Signed informed consent.

• Not pregnant (as proven by negative pregnancy test in case of woman of childbearing potential before first study drug administration) or breast-feeding.

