## 4.1 DIZZINESS HANDICAP INVENTORY

The DHI is a validated, self-report questionnaire which is widely used as an outcome measure. It assesses precipitating physical factors associated with dizziness/unsteadiness and functional/emotional consequences of symptoms. To assess the impact of impairment, the patients are asked to fill out the 25 item DHI questionnaire, which has been used in previous studies for patients with vertigo of various origin. The scale has three sub-domains (physical, functional, and emotional questions).

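### The confidence-interval half-widths behind 20 BVP and 40 FD patients rest on an SD of 0.8 with no endpoint or unit, so the plan does not state the precision of its primary endpoint, change in DHI total

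*Protocol*

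**What the plan says.** The primary endpoint is change from baseline to month 2±1 in the total score ("Inventory (DHI; total", Protocol summary). Protocol 3.4 gives the scale and entry window: "DHI [0 (minimum score) -100 (maximum score)] between 30 to 90 points".

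The sample size paragraph appears in the Protocol summary, in Protocol 8 (Sample Size Calculation) and in SAP 5.1. All three give half-widths of 0.351 at n=20, 0.314 at n=25, 0.265 at n=30 and 0.248 at n=40 for a paired mean difference. The n=30 entry reads "n=30 (33 with 10% drop-out) distance from mean to limit 0.265". The inputs include "Standard deviation of 0.8 for both indications" and a power of 80%.

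An SD of 0.8 has a described origin only in the Protocol summary and Protocol 1.1, which report for an earlier trial against betahistine "a reduction of 2 score points of the mean intensity of vertigo attacks with a standard deviation of 0.8 score points".

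On attrition, the Protocol summary has "Lost to follow-up 10% (BVP) or 20% to 30% (FD"). Protocol 8 and SAP 5.1 give a single 10%. Protocol 3.2 adds that a patient who "does not complete the observational period may be replaced if study entry by end-April 2022".

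Protocol 8 and SAP 5 and 5.4 say that the study is descriptive and tests no hypothesis.

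**The concern.** The sample size paragraph is the plan's only quantitative support for 20 and 40. A half-width is informative only if the reader knows what it measures. Here it should be points of mean DHI change, but neither the SD nor the half-widths carry a label, and the one labelled 0.8 belongs to a different outcome. A reader who takes 0.351 and 0.248 as DHI points would credit the study with a precision that the documents do not support.

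Three further entries in the same paragraph do not hold together: a power with no test, two different FD loss assumptions, and a half-width that does not fit its n. What is at stake is the stated justification for the group sizes, not the validity of any analysis.

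**Working it through.** **1. Reproducing the stated half-widths.** The inputs are SD 0.8 and two-sided 95% (Protocol 8, SAP 5.1). No formula is printed. Taking 0.8 as the SD of the paired difference, half-width = 1.96 × 0.8/√n = 1.568/√n.

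| n | 1.568/√n | Stated | t-based |
|---|---|---|---|
| 20 | 0.351 | 0.351 | 0.374 |
| 25 | 0.314 | 0.314 | 0.330 |
| 30 | 0.286 | 0.265 | 0.299 |
| 40 | 0.248 | 0.248 | 0.256 |

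Three of the four match the normal formula and none matches the t formula. Solving 1.568/√n = 0.265 gives n = (1.568/0.265)² = 35.0, so the n=30 entry carries the value for n=35. The same figure stands in all three places.

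**2. What the 0.8 refers to.** The endpoint is DHI total, scored 0 to 100. The only sourced 0.8 is in score points of attack intensity. No SD of DHI change appears in either document. The same 0.8 is used for both indications, although Protocol 8 explains the larger FD group by the heterogeneity of that disease.

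**3. Power.** A power needs a test and a target difference. The documents exclude testing and give no target difference for this study. The 80% therefore refers to nothing.

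**4. Loss to follow-up.** The planned inclusion of 20 and 40 equals the n used in the half-width calculation, so no allowance for loss is visible. The paragraph itself pairs 40 with 44 (40 × 1.1 = 44). Without replacement, the evaluable numbers are:

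- BVP, 10% loss: 20 × 0.9 = 18
- FD, 10% loss: 40 × 0.9 = 36
- FD, 20% loss: 40 × 0.8 = 32
- FD, 30% loss: 40 × 0.7 = 28

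**5. Size on the DHI scale.** The SD of DHI change is unknown, so the SDs below are hypothetical. Half-width = t(0.975, n−1) × SD/√n, in DHI points:

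| Group, evaluable n | SD 5 | SD 10 | SD 20 |
|---|---|---|---|
| BVP 20 (no loss, or all replaced) | 2.3 | 4.7 | 9.4 |
| BVP 18 | 2.5 | 5.0 | 9.9 |
| FD 40 (no loss, or all replaced) | 1.6 | 3.2 | 6.4 |
| FD 36 | 1.7 | 3.4 | 6.8 |
| FD 32 | 1.8 | 3.6 | 7.2 |
| FD 28 | 1.9 | 3.9 | 7.8 |

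The FD discrepancy alone (30% against 10% loss) gives 3.88/3.38 = 1.15, an interval about 15% wider. The unknown SD matters far more, because the half-width is proportional to it.

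**The case against.** The strongest reply is that the study is descriptive. The reported intervals will use the observed SD, n=30 is not a planned size, and no result or decision depends on this paragraph. All of that stands, and it is why the point is minor. It does not rescue the paragraph: the plan chose to justify its size by precision, and the figures given cannot be read for its own primary endpoint.

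Several stronger readings are tempting but not supported:

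- **That 0.8 was taken from the earlier trial.** This is a reasonable inference, since no other source is described, but the documents do not state the link.
- **That 0.8 is impossible for DHI change.** It looks very small for a 0-100 score built from a "25 item DHI questionnaire", but a proof would need the item scoring, which the documents do not give. The missing endpoint and unit are enough.
- **That 20 and 40 might mean evaluable patients.** The Protocol summary and SAP 5.4 speak of patients to be included, so they are enrolment numbers. What is missing is a visible loss allowance, partly offset by optional replacement.
- **That the SAP will not report mean DHI change.** SAP Table 14.2.1 describes DHI by answer category and shift table without naming the total. However, SAP 5.4 prescribes means and CIs for continuous variables and defines the FD and BVP subgroups, SAP 5.6.2 defines change from baseline, and Appendix 1 lists DHI as primary.
- **That the normal formula is an error.** Using t widens the interval by about 7% at n=20 (0.374/0.351) and 3% at n=40 (0.256/0.248). Either is acceptable for planning.

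**Conclusion.** The point holds as a minor defect: the paragraph is wrong as written, in all three places. The half-widths of 0.351 and 0.248 do not state the precision of mean change in DHI total, and that precision cannot be computed from the documents. The power entry has no referent, FD loss to follow-up is contradictory, and 0.265 at n=30 should be 0.286 if the formula behind the other three figures was intended.

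This rests on two assumptions: that 0.8 is meant as the SD of the paired difference, which three of the four figures bear out, and, for the DHI half-widths, on SDs that are illustrations only. A reader might infer that the study is too small or that its results will be unreliable. The documents support neither: they set no precision target, and the final intervals do not use the 0.8.

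**What to change.** Keep enrolment at 20 and 40. In the Protocol summary, Protocol 8 and SAP 5.1:

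- Replace the 0.8-based half-widths with half-widths for mean change in DHI total, in points, by indication. Use a sourced SD of change, or a range of SDs marked as hypothetical. If any 0.8-based figure is kept, label its scale and correct n=30 to 0.286.
- Delete the 80% power entry for the current study.
- Reconcile FD loss to follow-up to one figure or range, and give precision at the resulting evaluable n: without replacement, BVP 18 and FD 36, 32 or 28 at 10%, 20% or 30% loss. Say how far replacement under Protocol 3.2 is relied on.
- Do not count on final-visit data (Protocol 6.4, termination of treatment) from patients who withdraw consent. Protocol 6 (Patient Confidentiality) ends data collection for a patient who wants to leave the study.

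Optionally, name the total score in SAP Table 14.2.1.

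The cost is a text change in three places and, if wanted, one table line. The sponsor must find an SD of DHI change or mark a range as hypothetical, and commit to one FD loss assumption. No extra patients are needed. Two of the three places are in the observational plan, which goes to the authorities and an ethics committee (Protocol 1.1); the documents do not say what an amendment would require.
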